#### **12.4.7.2 Interim analyses**

No formal interim analyses are planned.

An overall study report will be written after completion of OLEX, giving the efficacy and safety results of the entire study.

#### **12.4.7.3 Data monitoring committee**

An independent DMC will be assigned to monitor subject’s safety throughout the clinical course of the study (see [Appendix 16.2](#)). It will consist of an uneven number of physicians, e.g., three physicians, to achieve a decision of majority. DMC members must be experienced in the indication and population and will not be involved in any study conduct sponsored by Merz. An independent biostatistician may complement the DMC. The primary purpose of the DMC is to safeguard subject. The DMC provides a mean to rapidly note an unexpected hazard that may lead to study termination.

The DMC will meet at regular intervals during MP and OLEX to discuss and decide upon safety issues. The treatment code of individual subjects may be unblinded by the DMC if necessary for evaluation purposes (see [Section 8.3.2](#)).

If indicated, the DMC will make recommendations regarding withdrawals, and/or measures for the study in case of relevant safety findings. Details on responsibilities and procedures to be followed by the DMC will be laid down in the DMC Charter.

#### **12.4.7.4 Multiple comparisons/multiplicity**

Due to the hierarchical testing strategy described, no further alpha-adjustment for multiple testing is necessary as it ensures the overall type I level of 5% for the confirmatory tests. Please see [Section 12.4.1.1](#) for details.

#### **12.4.7.5      *Examination of subgroups***

Subgroup analyses will be performed for the AS regarding treatment group, site (or pooled sites), BoNT-A pre-treatment status, GMFCS level groups at baseline, and AS baseline value. In addition, subgroup analysis for the AS regarding subjects with unilateral and bilateral treatment will be performed. If applicable, the influence of these subgroups will also be analyzed for the other efficacy variables. Potential effects of the use of local anesthetics and/or analgosedation on AS and adverse event/adverse events of special interest will be analyzed descriptively.

Details of subgroup analyses and additional subgroup analyses (e.g., gender, dose group, age, group [2-5, 6-11, 12-17 years], weight, height) will be specified in detail in the SAP.

## 13 DATA HANDLING AND RECORDKEEPING

By signing and dating the eCRF, the investigator will confirm that all investigations have been completed and conducted in compliance with the clinical study protocol, and that reliable and complete data have been entered into the eCRF.

### 13.1 Corrections to data

All data required by this clinical study protocol are to be recorded on eCRF (electronic data capture system [REDACTED]) as soon as possible. Direct entries are not allowed; data must be transcribed from the source (e.g., subject file) to the eCRF.

If corrections are necessary, an authorized member of the investigator's staff will enter the correct data in the web-based eCRF. The audit trail in [REDACTED] documents all changes. Edit checks issue automatic queries during data entry when a field is not populated to specifications defined in the DVP. Manual queries (to be answered by site staff) can be raised during source data verification, medical or safety review, and data management review.

The sponsor's data management function will be responsible for data processing, in accordance with the sponsor's data management procedures. Database close will occur only after quality control procedures have been completed.

### 13.2 Recordkeeping

Essential documents should be retained until at least 2 years after the last approval of a marketing application (whether pending or contemplated) in an ICH region, or at least 2 years have elapsed since the formal discontinuation of IP clinical development. These documents should be retained for a longer period, however, if required by applicable regulatory requirements or by agreement with the sponsor.

Essential documents at the investigational site include (among other documents):

- Subject's files.
- Subject's identification code list (i.e., provided by template to the investigator, along with the ISF, at the beginning of the study), which identifies the subject by number, name, and date of birth.
- A signed copy of the final clinical study protocol and any amendment.
- CD/DVD with eCRF data and any associated subject-related source data (or, where applicable, authorized copies of source data).
- Signed IC forms.

- Copies of site investigators' and co-workers' curricula vitae.
- Copies of all direct correspondence with the IEC/IRB and with the regulatory authority(ies).
- Copies of laboratory normal ranges and methods.
- Copies of study supply receipt forms and drug inventory forms.
- Copies of all correspondence between the investigator and the monitor, and between the investigator and the sponsor.
- Copies of safety information reported during the study and submitted by the sponsor.

### **13.3 Destruction of study documents**

Study documents may not be destroyed by study site personnel prior to the retention period specified above without the prior written consent of the sponsor. The PI must inform the sponsor in due time if the PI leaves the institution during the retention period. This rule also applies when the institution closes within the retention period.

## **14 PUBLICATION POLICY**

The study will be registered and study results will be disclosed by the sponsor (or delegate) in one or more public clinical study registry(ies) according to national/international regulations and relevant commitments of pharmaceutical industry associations. Study registration may include a list of the investigational sites.

The study results will be submitted for 1st full publication in an appropriate medical journal, and publishing details will be given in the clinical study agreement. The principal investigator of each site will be mentioned in the acknowledgement of the publication.

Further submission for publication (e.g., poster, journal) concerning study results after an initial full journal publication must be approved in advance by the sponsor in writing.

The results of this study and any discoveries related to this study, regardless of whether they have technical or medical character, are the property of the sponsor.

1 LIST OF ABBREVIATIONS

ANCOVA	Analysis of covariance
AS	Ashworth scale
ATC	Anatomical therapeutic chemical classification
BDRM	Blind data review meeting
BMI	Body mass index
BOCF	Baseline observation carried forward
BoNT	Botulinum Toxin
█	█
CP	Cerebral palsy
CSP	Clinical study protocol
C-SSRS	Columbia-Suicide Severity Rating Scale
eCRF	Electronic case report form
Desc. stat.	Descriptive statistics
DMC	Data monitoring committee
EMG	electromyography
e-stim	electrical stimulation
FAS	Full analysis set
Freq.	Frequency table
GICS	Global Impression of Change Scales
GMFCS-E&R	Gross Motor Function Classification System (expanded and revised version)
IV/WRS	Interactive voice (web) response system
LOCF	Last observation carried forward principle
LL	Lower limb
MAS	Modified Ashworth scale
MedDRA	Medical Dictionary for Regulatory Activities
MMRM	Mixed model repeated measures
MP	Main Period
n	Number of non-missing observations
Nexp	Number exposed
OLEX	Open-label extension
PBO	Placebo

PDF	Portable Document Format
PPS	Per protocol set
QPS	Questionnaire on Pain caused by Spasticity
SAP	Statistical analysis plan
SAS®	Statistical Analysis System software
SD	Standard deviation
SE	Standard error
SES	Safety evaluation set
SMQ	Standard MedDRA query
SOC	System organ class
TC	Telephone Contact
TEAE	Treatment emergent adverse event
TEAESI	Treatment emergent adverse events of special interest
TESAE	Treatment emergent serious adverse event
TFLs	Tables, figures and listings
UL	Upper limb
WHO	World health organization

2 GENERAL AND TECHNICAL ASPECTS

The objective of this statistical analysis plan is to specify the statistical analyses in more detail than stated in the clinical study protocol (CSP) and to be precise enough to serve as a guideline for statistical programming and creation of tables, figures and listings.

This statistical analysis plan is based on the clinical study protocol version 3.0, dated 07-APR-2016 and the following amendment no. 1, dated 24-APR-2015.

All programs will be written using Statistical Analysis System Software (SAS[®]) version 9.2 or higher. A font size of 10 points will be used for the tables and figures in section 14, corresponding to a line size of 111 digits and a page size of 42 lines for an output in A4 format. The font size of 10 points will also be used for all listings, if possible. If this is not possible, for listings, a minimum font size of 8 points with the line size of 140 points and page size of 52 lines will be used to produce the output in A4 format. Single SAS programs will be written for all tables and figures, and all listings, respectively. All outputs will be transferred into Portable Document Format (PDF)-files using the Merz internal SAS macro LST2PDF. These PDF-files will be generated separately for the tables and figures of section 14 and the listings of section 16.2 of the appendix of the clinical study report. Each PDF-file will include the corresponding table of contents, preceding the content of the file.

The standard tables, figures and listings (TFLs) will be applied.

3 CLINICAL STUDY DESIGN AND OBJECTIVES

3.1 Clinical Study Design

This is a prospective, multicenter, multi-national, randomized, double-blind, parallel-group, dose-response study in phase 3 of three doses NT 201. Subjects with upper limb spasticity alone or with combined upper limb (UL) and lower limb (LL) spasticity due to cerebral palsy (CP) will be treated. The study comprises a Main Period (MP) with a single double-blind treatment cycle with three dose arms (high, mid, low), followed by three open-label extension (OLEX) treatment cycles with a single treatment arm using the high dose regimen of MP. Each of the four treatment cycles has an observation period of 12 to 16 weeks, i.e. 14 weeks \pm 14 days.

Treatment of UL(s) in MP will be administered in three parallel dose groups of NT 201 with fixed doses to UL(s):

- In the high dose group 8 U/Kg BW NT 201 (maximum dose per UL: 200 Units (U) for subjects \geq 25kg BW).
- In the mid dose group 6 U/kg BW (maximum of 150 U) per UL.
- In the low dose group 2 U/kg BW (maximum of 50 U) per UL.

As clinically needed, UL treatment can be administered unilaterally or bilaterally and subjects may receive additional Botulinum Toxin (BoNT) injections in one out of five predefined treatment combinations (A-E) up to the maximum total dose applicable for their Gross Motor Function Classification System expanded and revised version (GMFCS-E&R) level (I-III: 20 U/kg BW NT 201, maximum of 500 U; IV and V: 16 U/kg BW NT 201, maximum of 400 U):

- Treatment Combination A: Unilateral or bilateral UL treatment only
- Treatment Combination B: Unilateral UL and unilateral LL treatment
- Treatment Combination C: Unilateral UL and bilateral LL treatment in GMFCS-E&R level I-III
- Treatment Combination D: Unilateral UL and bilateral LL treatment in GMFCS-E&R level IV-V
- Treatment Combination E: Bilateral UL and bilateral LL treatment in GMFCS-E&R level I-III

In MP only, LL(s) treatment will be performed within the same dose groups as UL treatment, i.e. subjects in the mid and low dose group will receive 75% or 25%, respectively, of the dose in the high dose group to all limbs treated.

A total of 344 subjects (2 : 1 : 1 ratio) will be enrolled with:

- At least 172 subjects randomized to the high dose group.
- At least 86 subjects to the mid dose group.
- At least 86 subjects to the low dose group.

The study includes the following visits:

Screening:

Screening Visit (V1): Day -14 (Week -2) ± 5 days

Main Period (MP):

Baseline Injection Visit (V2): Day 1, randomization

Telephone Contact (TC1): Day 8 (Week 1) ± 3 days of MP

Ctrl. Visit (V3): Day 29 (Week 4) ± 3 days of MP

Ctrl. Visit (V4): Day 57 (Week 8) ± 3 days of MP

Optional Telephone Contact
Wk12: Day 85 (Week 12) \pm 3 days of MP

Final Visit of MP (V5) Day 99 (Week 14) \pm 14 days of MP

Open-Label Extension Period (OLEX)

Injection Visit (V6, V10, V14): Day 1 of the 2nd to 4th treatment cycle.

Telephone Contact (TC)
(TC2, TC3, TC4): Day 8 (Week 1) \pm 3 days of 2nd to 4th treatment cycle.

Ctrl. Visit (V7, V11, V15): Day 29 (Week 4) \pm 3 days of 2nd to 4th treatment cycle

Ctrl. Visit (V8, V12, V16): Day 57 (Week 8) \pm 3 days of 2nd to 4th treatment cycle

End of Cycle Visit (V9, V13) Day 99 (Week 14) \pm 14 days of 2nd and 3rd treatment cycle

End of Study Visit (V17): Day 99 (Week 14) \pm 14 days of 4th treatment cycle.

Revisit for reinjection

If any eligibility criterion is not met either at the Final Visit of MP (V5) or at an End of Cycle Visit in OLEX (V9 or V13), the injection may be rescheduled within up to 16 weeks after the last injection treatment.

3.2 Clinical Study Objectives

The objectives of the study are to investigate efficacy and safety of NT 201 in children (age 2-11 years) and adolescents (age 12-17 years inclusive) with UL spasticity alone or with combined UL and LL spasticity due to CP.

4 DETERMINATION OF SAMPLE SIZE

The sample size estimation for the primary efficacy variable 'change from baseline in AS in the primary clinical target pattern, i.e. elbow flexors or wrist flexors, at Day 29 (Week 4)' was based on data of a study with BoNT-A in the treatment of post-stroke UL spasticity in adults [Childers 2004 (1)]. In this trial a modification of the original 5-point AS to a 9-point scale by adding 4 half point increments was used. Since this modified Ashworth Scale (MAS) is very similar to the original Ashworth Scale (AS) used in the present study, it appeared to be justified to base the sample size calculation on the MAS results of the study by Childers et al.. In this study, a mean change from baseline in MAS scores at the elbow of -1.01 in the 180 U BoNT-A dose group and of -0.7 in the 90 U dose group were observed. It was assumed that the changes from baseline in AS for flexed elbow will be comparable to the one for flexed

wrist. The 180 U dose lies between the 200 U and the 150 U (for subjects ≥ 25 kg) doses planned for the high and mid dose group in this study. Since published trial data for the exact doses planned in this trial did not exist, and doses of BoNT-A applied in spasticity show complex non-linear correlations to AS scores [Yablon 2011 (2)], it appeared to be justified to use the same assumptions for both dose groups.

Comparable Placebo (PBO)-controlled studies showed a low drop-out rate of 3% at the time of assessment of the primary efficacy variable. Therefore, a similarly small number of missing data for the primary efficacy endpoint was expected for this study. Consideration of assumptions above with a 3% rate of missing values and using last observation carried forward (LOCF) as originally planned in the CSP led to the group means $\mu_{NT201_high} = -0.98$, $\mu_{NT201_mid} = -0.98$ and $\mu_{NT201_low} = -0.68$.

The assumption for a pooled common standard deviation (SD) was $\sigma = 0.6$.

An estimated total number of 258 (with randomization ratio of 2:1) subjects will provide 96.5% power to show a statistically significant difference between the NT 201 high dose group (172 subjects) and the NT 201 low dose group (86 subjects) at an alpha level of 0.05 (two-sided t-test, Statistical Analysis System software[®]).

An estimated total number of 172 subjects (with randomization ratio of 1:1) will provide 90.3% power to show a statistically significant difference between the NT 201 mid dose group (86 subjects) and the NT 201 low dose group (86 subjects) at an alpha level of 0.05 (two-sided t-test, Statistical Analysis System software[®]) in the primary efficacy variable.

For the co-primary efficacy variable 'Investigator's Global Impression of Change Scale (GICS) 4 weeks after injection', data from [Childers 2004 (1)] were used as well. In this study, a 9-point global assessment scale ranging from +4 (very marked improvement) to -4 (very marked worsening) was used to assess the response to treatment. In the group treated with 180 U Botulinum Toxin Type A, the mean response to treatment rated by the subject at week 3 was 1.4 points with a standard deviation of 1.0 points. Given that only PBO values for the global assessment scale were reported and since no global response compared to PBO had been detected in the 90 U dose group, data from the PBO group were used here. In the PBO group, the corresponding point estimator for the mean value was 0.8 points with a standard deviation of 0.8 points. It was assumed that the 9-point scale has a comparable effect size to the 7-point scale used in this study.

When conservatively accounting for missing data of about 3% and considering the required $N=258$ (randomization ratio 2:1) subjects for the treatment comparison of the primary efficacy variable, a mean treatment response difference of 0.582 points with a pooled common standard deviation of 1 will still provide 99.2% power to show statistically significant superiority in the co-primary variable in favor of NT 201 high dose group versus low dose group.

An estimated total number of $N=172$ subjects (with randomization ratio of 1:1) will provide 96.7% power to show a statistically significant difference between the NT 201 mid dose

group (86 subjects) and the NT 201 low dose group (86 subjects) at an alpha level of 0.05 in the co-primary efficacy variable.

It is estimated that the sample size of N=344 subjects will provide 95.7% power (product of the single power calculations for both the primary and the co-primary efficacy variable for the high versus low dose treatment comparison) to show a statistically significant difference between NT 201 high dose and NT 201 low dose group. A power of 87.3% is provided for the treatment comparison of the mid versus the low dose in both primary and co-primary efficacy variables.

Using a randomization ratio of 2:1:1 at least 172 subjects were planned to be randomized to the NT 201 high dose treatment group, at least 86 subjects were planned to be randomized to the NT 201 mid dose treatment group and at least 86 subjects were planned to be randomized to the NT 201 low dose treatment group.

5 ANALYSIS SET

The following analysis sets will be defined for the statistical analysis of the Main Period of this clinical study:

Safety Evaluation Set (SES) of the Main Period

The SES of the Main Period is the subset of all subjects who receive study medication in the MP at least once.

Full Analysis Set (FAS) of the Main Period

The FAS of the MP is the subset in the SES of the MP for whom the primary efficacy variable or co-primary efficacy variable is available, i.e. all subjects who have at least either an AS score in the clinical pattern flexed elbow or flexed wrist at baseline (Day 1), or the Investigator's GICS for upper limb at Day 29 (Week 4).

Per Protocol Set (PPS) of the Main Period

The PPS is the subset in the FAS of the MP without major protocol deviations. Major protocol deviations will be defined during the Blind Data Review Meeting (BDRM).

The following analysis sets will be defined for the statistical analysis of the OLEX period of this clinical study:

SES of the OLEX Period

The SES is the subset of all subjects who receive study medication at least once during the OLEX period.

FAS of the OLEX Period

The FAS is the subset of subjects in the SES of the OLEX for whom at least one post-baseline value of any efficacy variable in the OLEX is available.

Subjects which have not been treated according to the randomization list in the MP will be excluded from PPS of the MP. If subjects have not been treated according to the randomization list in the MP, tables performed on the SES will be analyzed as treated for the MP treatment group and tables performed on the FAS will be analyzed as randomized for the MP treatment group. If subjects have been treated with MP medication in the OLEX they will be analyzed regularly according to their planned high dose treatment of the OLEX regardless if they actually received low, high or mid dose. In the subject data listings the MP treatment group will be listed as randomized except for the section 16.2.7 and 16.2.8, here the actual MP treatment group will be listed.

6 VARIABLES FOR ANALYSIS

6.1 Efficacy Variables

6.1.1 Primary Efficacy Variable

The primary efficacy variable will be determined for MP only.

- Primary efficacy variable is the change from baseline in AS in the primary clinical target pattern, i.e. elbow flexors or wrist flexors, at Day 29 (Week 4) of MP.

For subjects with bilateral UL treatment, the body side for analysis will be decided by the investigator at screening. If both main clinical target patterns elbow flexors and wrist flexors are qualified for primary efficacy analysis, an interactive voice (web) response system (IV/WRS) will select the primary clinical target pattern. The primary clinical target pattern will be set to missing for subjects whose primary clinical target pattern was not treated in the MP by mistake. As a consequence these subjects will not have the primary efficacy variable “change from baseline in AS in the primary clinical target pattern”.

The AS is a well-known and validated scale to categorize the severity of spasticity by judging resistance to passive movement. Spasticity will be assessed separately for elbow flexors, wrist flexors, forearm pronators, finger flexors and thumb flexors if chosen for BoNT injection on the following 5-point scale:

- 0 = no increase in tone
- 1 = slight increase in tone giving a “catch” when the limb was moved in flexion or extension.
- 2 = more marked increase in tone, but limb easily flexed.
- 3 = considerable increase in tone - passive movements difficult.

4 = limb rigid in flexion or extension

In order to be enrolled, subjects must have an AS score of ≥ 2 points for elbow flexors and/or wrist flexors in at least one UL. For initiation of treatment in this study, all chosen clinical patterns (UL and LL) must have an AS score ≥ 2 at the Baseline Injection Visit V2 of MP.

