### **8.2.1 Methods of assigning subjects to treatment groups**

The study is planned as an international multi-center study. At the Baseline Injection Visit (Day 1) of the double-blind MP, subjects will be assigned to one of three dose groups of NT 201 (high, mid, and low) according to a 2 : 1 : 1 randomization scheme.

Randomization will be balanced in blocks of appropriate size. The distribution of the IP to the investigational sites and the randomization will be controlled by IV/WRS to ensure a number of enrolled subjects approximately according to the randomization ratio of 2 : 1 : 1 in the three treatment groups. Subjects discontinued from the study will not be replaced.

In this study, two main clinical target patterns have been defined, i.e. *flexed elbow* with an assessment of the AS score for elbow flexors and *flexed wrist* with an assessment of the AS score for wrist flexors. Randomization will be stratified by primary clinical pattern (elbow flexors/flexed wrist) in a 1:1 ratio within each dose group.

In practice, a subject may have up to two main clinical target patterns qualifying for primary efficacy analysis based (a) on the clinical need for IP injection and (b) on the presence of an AS score  $\geq 2$  in elbow or wrist flexors. Since no clinical algorithm is existent to decide which of both main clinical target patterns to take for primary efficacy analysis in such a situation, an IV/WRS will be used to achieve an overall equal distribution of primary clinical target patterns flexed elbow and flexed wrist in this study. The selection will be performed by the IV/WRS before randomization to treatment groups (i.e. to one of three dose groups of NT 201 in MP). In case only one main clinical target pattern qualifies for primary efficacy analysis, this pattern will be selected by the IV/WRS. If both main clinical target patterns would qualify for primary efficacy analysis,

the selection has to be in a way that after randomization the distribution of primary clinical target patterns is balanced as much as possible in both treatment groups, or at random, if this is not possible.

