It is mandatory for the investigator to assess the clinical patterns flexed elbow, flexed wrist, and clenched fist in the UL(s) selected for treatment. This means, that for unilateral UL treatment, these three patterns of the treated body side have to be assessed, whereas for bilateral treatment the three respective clinical patterns of both ULs have to be evaluated with the AS. Furthermore, the AS has to be utilized for each other treated UL or LL clinical pattern, such as thumb in palm, pronated forearm, pes equinus, flexed knee, and adducted thigh. An exemption is the clinical pattern extended great toe, for which no AS assessment has to be documented.

Limb positioning for each AS assessment will be described in an instructional outcome manual, must be documented with the AS assessment and also recorded in the eCRF. The limb positioning chosen for AS testing by the investigator in an individual subject at V2 has to be kept throughout study participation. Reasons for deviations from the initially chosen positioning e.g. newly developed contractures have to be documented in the eCRF.

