
For efficacy variables the last measurement before start of treatment is defined as baseline value.

Testing of the primary, co-primary and key-secondary efficacy variables of the MP will be performed in a 4-step approach using a hierarchical test procedure as described below:

1. Step: Primary and co-primary efficacy variables for high dose vs. low dose.
2. Step: First key-secondary efficacy variable and co-primary efficacy on subpopulation variables for high dose vs. low dose.
3. Step: Second key-secondary efficacy variable for high dose vs. low dose.
4. Step: Primary and co-primary efficacy variables for mid dose vs. low dose.

Due to the hierarchical testing strategy of (co-)primary and key-secondary efficacy variables and the two dose group comparisons (high versus low and mid versus low), this four step hierarchical testing procedure ensures the overall type I level of 5% for the confirmatory tests. If one of four hierarchical tests does not yield a statistically significant result, the consecutive test(s) will still be performed but will be considered to be only descriptive.

The estimand of interest of this study is the treatment effect measured by the primary and co-primary efficacy variables in all subjects of FAS of the MP regardless of adherence to randomization list.

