7.7 Special Statistical/Analytical Issues

7.7.1 Discontinuations and Missing Data

Discontinued subjects will not be replaced.

The primary and secondary efficacy variables of the Ashworth scale score will be analyzed on the FAS and PPS of the MP using MMRM for accounting for missing data. The model will be based on the observed cases data without imputing missing values. As sensitivity analysis for the primary efficacy variable and for the secondary efficacy variables of the AS score an ANCOVA model without repeated measures will be applied. The LOCF principle will be followed on the FAS and PPS of the MP, i.e., the last observation (including baseline) will be carried forward to Week 4 and all further visits with missing values. In addition, further sensitivity analysis for the primary and secondary efficacy variables, the so called observed case analysis without missing data replacement, will be performed on the FAS and PPS of the MP to explore the impact of the respective missing imputation principle.

In case of missing data in the co-primary variable these will be imputed by “0” (no change). Assuming a similar percentage of missing data in all three treatment arms this imputation

leads to a decreased difference of the treatment effects. For this reason the “no change” imputation is considered as conservative approach.

As the GICS is only measured at Control Visit V3, it is not possible to apply a model based analysis like mixed model repeated measurement. Therefore, only ‘no change replacement’ and observed case analysis as sensitivity analysis will be performed.

For the secondary efficacy variable ‘Questionnaire on Pain caused by Spasticity’ LOCF and observed case analyses will be performed on the FAS and the PPS. For the secondary efficacy variable ‘Global Impression of Change Scales’ missing values will be replaced by “0” (no change) and an observed case analyses will be performed on the FAS and the PPS.

For child’s/adolescent’s GICS and QPS the observed case analysis is the main analysis of interest, and the ‘no change replacement’ (GICS) and the LOCF (QPS) are the respective sensitivity analyses.

Missing assessments except for primary or co-primary efficacy variable will not be listed as protocol deviations.

Observed case analysis will be performed for all efficacy data of the OLEX period, i.e. missing data of the OLEX will not be replaced.

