The primary clinical target pattern will be set to missing for subjects whose primary clinical target pattern was not treated in the MP by mistake. As a consequence these subjects will not have the primary efficacy variable "change from baseline in AS in the primary clinical target pattern". If these subjects have a measurement for the Investigator's GICS for upper limb at Day 29 these subject still belong to the FAS of the MP. According to the definition of the FAS of the OLEX from the CSP, subjects without primary clinical target pattern will be excluded from the FAS of the OLEX. But it is more reasonable to evaluate all subjects for the OLEX for whom at least one post-baseline value of any efficacy variable in the OLEX is available. In agreement with the intention-to-treat principle the Full Analysis Set of the OLEX should be as "full" as possible. For this reason the definition of the FAS of the OLEX will be changed to the following definition: The FAS of the OLEX is the subset of subjects in the SES of the OLEX for whom at least one post-baseline value of any efficacy variable in the OLEX is available. As a consequence subjects without primary clinical target pattern will no longer be excluded from the OLEX.

Investigator's, Child's/Adolescent's (if applicable) and Parent's/Caregiver's GICS [REDACTED] will be analyzed by descriptive summary statistics and frequency tables [REDACTED] instead of analysis of covariance (ANCOVA) for the OLEX Period. An ANCOVA is not appropriate for the OLEX period since all subjects receive the same treatment and no treatment differences can be estimated.

Other efficacy variables:

For other efficacy variables in the SAP the visit numbers were added and the variables were given in more detail than in the protocol.

Further other variables:

Planned treatment of spasticity, treatment compliance, monitoring during sedation, injection guidance technique, length of injection cycle, and extent of exposure were added to other variables.

Safety variables:

The secondary efficacy variable occurrence of TEAEs by final outcome in the CSP was changed to occurrence of TEAEs by worst outcome in the SAP. Usually final outcome is the same as worst outcome. But it may occur that a subject has two different TEAEs at two different time points, which are coded with the same PT (e.g. left leg broken and right leg broken). Then it is more important to know the worst outcome of both TEAEs than only the outcome of the second TEAE.

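### The primary Ashworth outcome is deleted when the selected pattern was missed at injection, which does not fit an estimand covering all FAS subjects

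*SAP*

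**What the plan says.** The rule is in SAP 6.1.1: "The primary clinical target pattern will be set to missing for subjects whose primary clinical target pattern was not treated in the MP by mistake". The SAP adds that such subjects then lack the primary variable, and it repeats the rule in section 8.

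SAP 7.1 defines the estimand as "the treatment effect measured by the primary and co-primary efficacy variables in all subjects of FAS of the MP regardless of adherence" to the randomisation list. SAP 5 states that "tables performed on the FAS will be analyzed as randomized for the MP treatment group".

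On timing, Protocol 8.2.1 says of the primary pattern: "The selection will be performed by the IV/WRS before randomization to treatment groups". This includes subjects with only one qualifying pattern. Protocol 9.2 places the first injection after randomisation.

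On data collection, Protocol 9.1.1.1 says: "It is mandatory for the investigator to assess the clinical patterns flexed elbow, flexed wrist, and clenched fist in the UL(s) selected for treatment". SAP 6.1.1 lists the upper-limb muscle groups to be scored and ends the list with "if chosen for BoNT injection on the following 5-point scale".

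On analysis, SAP 7.1.1 runs the confirmatory MMRM on the FAS, and SAP 7.7.1 says: "The model will be based on the observed cases data without imputing missing values". SAP 8 says that affected subjects with a Day 29 upper-limb Investigator's GICS are kept: "these subject still belong to the FAS of the MP".

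**The concern.** Deleting the outcome because the selected pattern was not injected removes a randomised subject from the primary variable on the basis of something that happened after allocation. The confirmatory AS estimate then describes FAS subjects whose selected pattern was injected, while SAP 7.1 labels it as the effect in all FAS subjects. Nothing in the readable text connects the two statements.

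The two step 1 tests can also rest on different subjects, because affected subjects leave the AS test but stay in the GICS test if they have a Day 29 upper-limb rating. Step 1 opens the whole four-step hierarchy. If uninjected patterns change equally in all arms, dropping them gives a somewhat larger AS difference than the stated estimand would.

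**Working it through.** **Does any listed analysis bring these subjects back?** (SAP 6.1.2, 7.1.1, 7.7.1)

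- MMRM: observed cases only. With no primary pattern there is neither an outcome nor a baseline covariate.
- LOCF, which at Week 4 equals carrying baseline forward: it needs the primary-pattern baseline, which is also undefined.
- Observed-case and Wilcoxon analyses: they use the same variable.
- PPS: a subset of the FAS using the same variable.
- Secondary AS variables: defined for treated patterns only.

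None restores them.

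**Inputs.** From SAP 4: mean AS change −0.98 (high), −0.98 (mid), −0.68 (low); SD 0.6; two-sided alpha 0.05; 172, 86 and 86 subjects. The documents give neither the share affected, f, nor the response of an uninjected pattern. Assumed here: f = 1%, 3% or 5% in every arm (258 × f = about 3, 8 or 13 of the high and low subjects) and zero mean change in the uninjected pattern.

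**Reproducing the plan.** Two-sample t-test, noncentral t, difference 0.98 − 0.68 = 0.30: power is 96.5% for 172 vs 86 and 90.3% for 86 vs 86. Both match SAP 4.

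**Excluded (SAP rule).** n(1 − f) per arm, difference 0.30, SD 0.6.

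**Retained (all FAS).** Full n, difference 0.30(1 − f), and arm variance

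(1 − f) × 0.36 + f × s0² + f(1 − f) × mean²,

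where s0 is the SD of change in uninjected patterns. The low end of each range takes s0 = 0.6; the high end simply holds the SD at 0.6.

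Example, f = 5%, s0 = 0.6:
- high: 0.342 + 0.018 + 0.0475 × 0.9604 = 0.4056
- low: 0.342 + 0.018 + 0.0475 × 0.4624 = 0.3820
- pooled SD, high and low: √[(171 × 0.4056 + 85 × 0.3820)/256] = 0.631
- difference: 0.30 × 0.95 = 0.285, giving 92.6% power

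With s0 = 0 the pooled SD is 0.616 and power is 93.7%.

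| f | Difference retained (excluded: 0.30) | High vs low: retained / excluded | Mid vs low: retained / excluded |
|---|---|---|---|
| 1% | 0.297 | 95.9–96.2% / 96.3% | 89.2–89.8% / 90.0% |
| 3% | 0.291 | 94.4–95.5% / 96.0% | 86.8–88.5% / 89.4% |
| 5% | 0.285 | 92.6–94.8% / 95.7% | 84.2–87.2% / 88.8% |

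**Other assumptions at f = 5%.** If uninjected patterns improve by 0.3 or 0.6 points in both arms (s0 = 0.6), the difference is still 0.285 and high vs low power is 93.8% or 94.5%.

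**Unequal rates.** With zero change in uninjected patterns, 5% affected in the high arm and none in the low arm gives 0.98 × 0.95 − 0.68 = 0.251. The reverse gives 0.98 − 0.68 × 0.95 = 0.334. The blinded design makes such an imbalance unlikely.

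**For scale.** The planned means already contain a 3% zero-change allowance for drop-out under LOCF: −1.01 × 0.97 = −0.98 and −0.70 × 0.97 = −0.68. The MMRM no longer imputes that.

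**The case against.** The strongest reply is that the SAP implicitly asks a different, legitimate question: what the effect would be had the selected pattern been injected. The FAS admits subjects with either the primary or the co-primary variable, so members without an AS value are expected. The adherence phrase in the estimand concerns the assigned arm and says nothing about an uninjected pattern. If mistakes are unrelated to arm, an MMRM without these values could be read as targeting that hypothetical effect. The other AS endpoints are also limited to treated patterns. The rule is stated twice, applies to every arm and was set for a blinded period. GICS must also be significant, and affected subjects with a rating remain in that test. The likely effect is small.

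Much of this stands. No bias is shown, the conflict is only with the words covering all FAS subjects, and the size is modest and hypothetical. The phrase in SAP 6.1.1 about patterns chosen for injection may be meant to qualify only the optional patterns, so it is a wording conflict and does not cancel mandatory scoring. Parts of the SAP on other efficacy variables are redacted, so the absence of a further analysis is established only for the readable text.

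It does not dispose of the point. The hypothetical reading appears nowhere in the SAP, and disclosing a rule does not reconcile it with the estimand. The GICS test does not recover the AS estimate.

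**Conclusion.** The concern holds. The SAP removes the primary AS value because of a post-randomisation injection mistake while declaring an estimand over all FAS subjects, and no readable analysis shows the difference. It should be corrected, but it does not threaten the trial. At an assumed 5% affected per arm with equal mean change across arms in uninjected patterns, the estimate differs by 0.30 − 0.285 = 0.015 AS points. Under zero mean change, retaining these subjects costs about 1 to 3 points of power for high vs low and about 1.6 to 4.6 points for mid vs low. At 1% the shift is 0.003 AS points. The true count and the response of uninjected patterns are unknown, so these figures illustrate a range.

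**What to change.** For the primary variable only, analyse the recorded AS of the IV/WRS-selected pattern for every FAS subject as randomised, whether or not it was injected. Move the exclusion of mistakenly uninjected patterns to a named sensitivity analysis and/or the PPS, and report the number affected per arm. Align the scoring sentence in SAP 6.1.1 with the mandatory elbow and wrist assessment in Protocol 9.1.1.1. Leave the key-secondary variables restricted to treated patterns.

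This is a change to SAP text before unblinding and uses data the protocol already requires. If such subjects exist, the primary estimate may be slightly smaller, with the power cost given above.
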